8.4.2 Mental Health and Substance Use

Mental health and substance use included: depression severity (measured by HAMD, ODSIS, BSI); Anxiety (measured by BAI, OASIS, BSI, SIAS); Drug abuse (measured by SIP-D); Alcohol abuse (measured by AUDIT); Mental health (measured using MINI); and suicidality (measured by SIDAS).

8.4.2.1 Continuous Measures

Analysis	Mental Health and Substance Use: depression severity; anxiety; drug abuse; alcohol abuse; suicidality
Analysis population	All participants
Endpoint	Scale values at 8 and 12 months of follow-up
Unit of analysis	Participant
Method of analysis	Linear mixed model assuming missing at random (MAR)
Handling of missing data	MAR assumption
Adjustment covariates	A priori covariates include: study site (NYC or Miami); baseline score
Type I error	5% (2-sided)
Control of type I error	To control the false discovery rate, we will use the Benjamini and

STATISTICAL ANALYSIS PLAN

	Hochberg (1988) method.
Treatment effect estimate	Marginal least square mean (LSM) with 95% confidence limits if there is no treatment by time interaction ($p < 0.10$); otherwise, LSM will be summarized for each treatment and timepoint.

Sensitivity analyses will be conducted to investigate the MAR assumption, such as methods that model jointly the missingness and outcome distributions (National Research Council, 2010).

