4.2 Secondary Outcomes

Condomless anal sex at 12 months (binary); Condomless anal sex at 8 and 12 months (count); Depression severity, as measured using the HAMD depression severity score, ODSIS, and BSI at 8 and 12 month time points; Anxiety, as measured by the BAI, OASIS, BSI, and SIAS at 8 and 12 month time points; Drug abuse, as measured by the SIP-D at 8 and 12 month time points; Alcohol abuse, as measured using by the AUDIT at 8 and 12 month time points; Mental health, as defined by odds of no longer having at least one *DSM-5* diagnosis (e.g., depression, anxiety) that was present at baseline still be present at 8 and 12 month time points based on the MINI (binary); Suicidality as measured by SIDAS at 8 and 12 month time points (continuous); Minority stress as captured by rejection sensitivity measured using RS, internalized homophobia measured using IHS and IAT; and sexual orientation concealment measured using SOCS at 4 and 8 month time points (continuous); Universal stress processes as captured by emotional regulation as measured by DERS, rumination as defined by RRS, assertiveness as measured by RAS, social support as measured by MSPSS, cognitive bias as measured by SRET, and impulsivity measured by Go/No-Go at 4 and 8 month time points (continuous).

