6.3 Power for Secondary Outcomes

For secondary outcomes (e.g., mental health, substance use), we will have 80% power to detect an effect size of 0.55 and 0.70 for ESTEEM vs. CMHT and ESTEEM vs. VCT-only, respectively, at a type I error rate of 0.01 (conservative due to multiple testing). These effect sizes are smaller than those found in the pilot ([name] et. al. 2015).

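### For the continuous secondary scales, a treatment-by-time pretest at p<0.10 decides whether the 8- and 12-month effects or one marginal mean are reported, so a partial fade can be hidden

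*SAP*

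**What the plan says.** SAP 8.4.2.1 covers depression severity, anxiety, drug abuse, alcohol abuse and suicidality. It gives the endpoint as "Scale values at 8 and 12 months of follow-up". SAP 4.2 defines the same outcomes in that way, for example "Depression severity, as measured using the HAMD depression severity score, ODSIS, and BSI at 8 and 12 month time points".

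The analysis is a linear mixed model under missing at random. On adjustment the table says "A priori covariates include: study site (NYC or Miami); baseline score". The treatment effect is a marginal least-squares mean with 95% limits "if there is no treatment by time interaction" at p<0.10; "otherwise, LSM will be summarized for each treatment and timepoint".

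The section leaves three things open. It does not say which visits the marginal mean averages, although these scales are also collected at 4 months. It attaches limits only to the pooled branch and names a between-arm difference in neither branch. It does not list the tests that enter the false discovery rate step.

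Other outcomes are handled differently. SAP 8.3.1 fixes the primary contrast at 8 months. SAP 8.4.1 (condomless anal sex at 12 months) and 8.4.2.2 (loss of a MINI diagnosis at 8 and 12 months) follow the primary method, with no pretest.

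**The concern.** The endpoints are two time-specific values, but a test on the data decides whether they are reported. An interaction test in a trial of this size has limited power against a moderate fade. A non-significant result is therefore weak evidence that the 8- and 12-month effects are equal, yet it triggers the replacement of both by their average.

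For a ten-session therapy completed within four months, the 12-month result is the evidence on durability. If benefit shrinks between 8 and 12 months, the average overstates what remains at 12 months and understates what was present at 8. If the effect is constant, the scales that cross p<0.10 by chance are reported by time point, with estimates selected for looking different. With ten scale scores (three for depression, four for anxiety, and one each for drugs, alcohol and suicidality), about 10 x 0.10 = 1 would switch by chance, so scales may be summarised on different quantities.

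**Working it through.** **Inputs from the SAP.** Evaluable numbers are 80 ESTEEM, 80 CMHT and 40 VCT-only (6.2). Planned secondary effects are 0.55 SD vs CMHT and 0.70 SD vs VCT-only at alpha 0.01 (6.3). The pretest is at 0.10, with two visits (8.4.2.1).

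**Assumptions, not in the documents.** Visit correlation r of 0.5 to 0.8, equal variances over time, residual SD 1, known-variance normal approximation, and the size of the fade.

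**Step 1: the plan's own figure.** SAP 6.3 states "we will have 80% power to detect an effect size of 0.55 and 0.70 for ESTEEM vs. CMHT and ESTEEM vs. VCT-only". For 80 vs 80, 0.55/sqrt(1/80+1/80) = 0.55/0.1581 = 3.479, and 3.479 - 2.576 = 0.903, so power is 0.817 (0.807 by noncentral t). For 80 vs 40, 0.70/0.1936 = 3.615, which gives 0.851 (0.838 by t). The CMHT figure reproduces, and the VCT-only figure is slightly conservative.

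**Step 2: how often a fade is pooled.** Let v = 1/n1 + 1/n2. The estimated fade has SE = sqrt(2v(1-r)), and the test misses when |Z| < 1.645.

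- 80 vs 80, r = 0.5, fade 0.30 (0.55 to 0.25): SE = 0.1581 and 0.30/0.1581 = 1.897. P(pool) = Phi(1.645-1.897) - Phi(-1.645-1.897) = 0.40.
- 80 vs 80, r = 0.8, same fade: SE = 0.10, ratio 3.0, P(pool) = 0.09.
- 80 vs 40, r = 0.5, fade 0.20 (0.55 to 0.35): SE = 0.1936, ratio 1.033, P(pool) = 0.73.

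**Step 3: coverage in one case (80 vs 80, r = 0.5, 0.55 to 0.25).** The pooled SE is sqrt(v(1+r)/2) = sqrt(0.025 x 0.75) = 0.1369. The pooled mean is off from either time-specific effect by half the fade, and 0.15/0.1369 = 1.095. Its limits cover the 12-month effect with probability Phi(1.96-1.095) - Phi(-1.96-1.095) = 0.805. Limits after a significant test cover 0.954 by simulation. Overall this is 0.40 x 0.805 + 0.60 x 0.954 = 0.894.

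With equal variances the average and the difference of the two estimates are independent. The pooled limits therefore keep 95% coverage of the average effect after a non-significant test.

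**Step 4: the range.** Simulation of the rule for one pair of arms, 400,000 draws per case, gives percent pooled / percent coverage of the 12-month effect:

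| Comparison and fade | r=0.5 | r=0.6 | r=0.7 | r=0.8 |
|---|---|---|---|---|
| 80 vs 80, 0.55 to 0.25 | 40 / 89.5 | 32 / 91.1 | 21 / 92.7 | 9 / 94.2 |
| 80 vs 80, 0.55 to 0.35 | 65 / 90.6 | 59 / 91.4 | 51 / 92.2 | 36 / 93.3 |
| 80 vs 40, 0.55 to 0.25 | 54 / 89.7 | 47 / 90.8 | 36 / 92.2 | 21 / 93.6 |
| 80 vs 40, 0.55 to 0.35 | 73 / 91.4 | 69 / 91.9 | 62 / 92.5 | 50 / 93.3 |

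Coverage of the 8-month effect is the same to within simulation error. A three-arm version with a 2-df interaction test gives pooling in 9-68% and coverage of 89-94%.

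**Step 5: other cases.**

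- Constant effect: overall coverage is 94.0-94.6%. Limits given after a significant pretest cover 85% (r = 0.5) to 91% (r = 0.8).
- Chance that the interval reported for 12 months excludes zero (80 vs 80, r = 0.5, 0.55 to 0.25): 47% under the rule. If the 12-month contrast is always reported it is Phi(0.25/0.1581 - 1.96) = Phi(-0.379) = 35%.
- Complete fade from 0.55 to 0: pooled in 3.4% (r = 0.5) to 0.2% (r = 0.7) vs CMHT, and in 12% to 2% vs VCT-only.
- If month 4 also enters the mean (three arms; 0.55, 0.55, then 0.275 at 12 months): 12-month coverage vs CMHT is 0.83 at r = 0.5, 0.86 at 0.6 and 0.93 at 0.8.

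**Step 6: without the pretest.** Always reporting both contrasts gives 95% coverage and no bias in every case.

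**The case against.** The strongest reply is that the 95% limits SAP 8.4.2.1 actually promises belong to the marginal mean, and they cover its target, the average effect, at 95%. That stands. A reader might infer that the stated limits are simply wrong. The documents do not support this: under-coverage appears only when the pooled interval is read as the 8- or 12-month effect. The SAP does not say it will be read that way, but 4.2 and 8.4.2.1 offer no other endpoint for it to answer. The 85-91% figure likewise presumes that limits are attached in the second branch, where the SAP says only "otherwise, LSM will be summarized for each treatment and timepoint".

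A reader might also infer that any loss of effect would be missed. This fails for a complete fade from the planned 0.55 SD vs CMHT, which is pooled in 3.4% of trials or fewer.

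A 12-month false-positive rate of 9-10% can be produced, but it needs an effect of 0.4 SD at 8 months, zero at 12 and r = 0.5. That effect is not a planning value, and at r = 0.7 the rate is 6-7%. With no effect at all it is at most 6%. All are unadjusted rates, whereas the SAP applies false discovery rate control.

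It is also tempting to say that one false discovery rate family will mix different quantities. The SAP does not list the family, so this is possible but not shown.

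Finally, the correlation and the fade are assumed. At r = 0.8 coverage is 93-94%, a small loss.

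**Conclusion.** The point holds for the continuous secondary mental health and substance use scales only. The rule replaces the defined endpoints with an average whenever an interaction test of limited power is not significant, and no other section restores them. For a partial fade from 0.55 to 0.25-0.35 SD, pooling occurs in about 9-73% of trials and time-specific coverage is about 89-94%. With a constant effect the overall loss is about one percentage point or less, concentrated in the scales that cross p<0.10.

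These are ranges under assumed correlations of 0.5 to 0.8, equal variances and the planned evaluable numbers. They are not estimates for this trial. The mismatch between endpoint and reporting rule does not depend on them. The primary outcome, condomless anal sex at 12 months and the MINI outcome are not affected. The change is worth making but does not threaten the main conclusion of the trial.

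**What to change.** In SAP 8.4.2.1, remove the interaction test as a reporting rule. For every continuous scale, state that the between-arm differences (ESTEEM vs CMHT, ESTEEM vs VCT-only) at 8 and at 12 months will be estimated from one arm-by-time mixed model with baseline score and site, and reported with 95% limits whatever the interaction p-value. List both time-specific tests in the false discovery rate family. Keep the interaction test and any marginal mean as descriptive, and name the visits that the mean averages.

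The cost is SAP wording; no new data are needed. If the effect is truly constant, the limits are wider than pooled ones by a factor of sqrt(2/(1+r)): 1.15 at r = 0.5 and 1.05 at r = 0.8. The family also holds two tests per scale and comparison, where pooling would give one.

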8.4.2.2 Binary Measure

Use of the MINI to define having at least one diagnosis present at baseline, no longer present at follow-up. We will use method described above for the primary outcome and assess at 8 and 12 months.

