8.3 Analysis of Primary Outcome: HIV-Risk Behavior (Condomless Anal Sex)

8.3.1 Primary Analysis of Primary Outcome: Condomless Anal Sex

Analysis	Primary analysis of primary outcome: condomless anal sex in the absence of either PrEP or known undetectable viral load of HIV+ primary partners, measured with the TLFB, a semi-structured interview.
Analysis population	All enrolled participants
Endpoint	8-month as reported on TLFB
Unit of analysis	Participant
Method of analysis*	Generalized linear mixed model with a log (log-binomial) link using a contrast to test the comparison at the primary time point of 8 months adjusting for site and race/ethnicity (Wacholder 1986). We will conduct the comparison of ESTEEM versus VCT at 0.05 level; only if this test is statistically significant will we test ESTEEM versus CMHT at 0.05.
Handling of missing data	MAR assumption
Adjustment covariates	Study site (NYC or Miami).
Type I error	5% (2-sided)
Control of type I error	We will use a gatekeeping strategy. If the first comparison is significant at 0.05, then we will conduct the second comparison at 0.05.
Treatment effect estimate	Risk ratio with 95% confidence limits

*If the log-binomial approach fails to converge, we will use a modified log-Poisson model (Zou 2004).

Sensitivity analysis: This will only be conducted if baseline imbalance of covariates is found (see Section 7.2). Adjustment for baseline covariates not balanced at randomization.

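### The MINI diagnosis outcome can be read as either at least one baseline diagnosis gone or none remaining, its effect measure is inconsistent, and its model has no baseline diagnosis term

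*SAP*

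**What the plan says.** The outcome is defined three times in the SAP.

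- Section 4.2: "Mental health, as defined by odds of no longer having at least one" DSM-5 diagnosis (depression and anxiety are given as examples) "that was present at baseline still be present at 8 and 12 month time points based on the MINI (binary"). Section 8.4 repeats this sentence.
- Section 8.4.2.2: "Use of the MINI to define having at least one diagnosis present at baseline, no longer present at follow-up".
- Table 1 in section 4 names only the instrument and its timing.

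For the model, section 8.4.2.2 says "We will use method described above for the primary outcome and assess at 8 and 12 months". That method, in section 8.3.1, is a log-binomial mixed model whose effect estimate is given as "Risk ratio with 95% confidence limits". Its covariate row lists site alone. Its method row adds race/ethnicity. Neither row includes anything about baseline diagnoses.

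Other outcomes are treated differently. The continuous mental health and substance use measures (section 8.4.2.1) take as covariates "study site (NYC or Miami); baseline score", and the supportive count analysis (section 8.3.2) adjusts for the baseline number of sex acts. Section 8.2 says adjusted sensitivity analyses will be considered if key covariates are imbalanced, but does not name diagnosis count among them.

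**The concern.** Take a man with three baseline diagnoses who has lost one at 8 months. If the event is that at least one baseline diagnosis has gone, he is a success. If the event is that none remains, he is a failure. The two definitions agree only for men who entered with a single diagnosis. Entry requires any depressive, anxiety, or trauma- and stressor-related disorder and sets no upper limit, so several diagnoses per man are allowed.

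This is the plan's only psychiatric-diagnosis outcome, in a trial that enrols by diagnosis. While the wording stays open, the choice of definition, and of odds ratio or risk ratio, could be made after the data are seen. Under either definition the chance of the event depends on how many diagnoses a man started with, and the specified model does not use that number.

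**Working it through.** **No figure to reproduce.** The documents give no event rate, effect size or power for this outcome. SAP section 6.3 covers secondary outcomes only through standardized effects of 0.55 and 0.70. Everything numerical below is illustrative.

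**The wording.** Call *at least one baseline diagnosis gone* reading A and *no baseline diagnosis remains* reading B.

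- Section 8.4.2.2 leans to A. Its comma, however, lets the first clause be taken as the starting condition, which gives B.
- Sections 4.2 and 8.4 lean to B through their opening words, but the sentence then collides with its own later clause about diagnoses still being present.
- Neither text excludes the other reading.

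**Event probability by number of baseline diagnoses.** Let k be the number of baseline diagnoses and q the chance that each one resolves (assumed). If diagnoses resolve independently, A = 1 − (1 − q)^k and B = q^k. At q = 0.40:

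| k | A | B |
|---|---|---|
| 1 | 0.40 | 0.40 |
| 2 | 0.64 | 0.16 |
| 3 | 0.78 | 0.06 |
| 4 | 0.87 | 0.03 |

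A larger k raises the probability under A and lowers it under B.

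**Effect on the result.** Assume q = 0.50 vs 0.35 and 35/30/20/15% of men with 1/2/3/4 diagnoses.

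- A, q = 0.50: 0.35×0.50 + 0.30×0.75 + 0.20×0.875 + 0.15×0.9375 = 0.716
- A, q = 0.35: 0.35×0.35 + 0.30×0.5775 + 0.20×0.7254 + 0.15×0.8215 = 0.564
- Risk ratio under A: 0.716/0.564 = 1.27
- B, q = 0.50: 0.35×0.50 + 0.30×0.25 + 0.20×0.125 + 0.15×0.0625 = 0.284
- B, q = 0.35: 0.35×0.35 + 0.30×0.1225 + 0.20×0.0429 + 0.15×0.0150 = 0.170
- Risk ratio under B: 0.284/0.170 = 1.67

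**Odds against risk.** From the same figures, the odds ratio under A is (0.716/0.284)/(0.564/0.436) = 1.9, against a risk ratio of 1.27. Under B it is (0.284/0.716)/(0.170/0.830) = 1.9, against 1.67. The effect measure therefore changes the reported number by as much as the definition does.

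**If diagnoses in one man resolve together.** A beta-binomial version with within-person correlation 0.6 gives 0.587 vs 0.431 under A (risk ratio 1.36) and 0.413 vs 0.272 under B (1.52). The gap narrows but does not close.

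**Value of the covariate.** Across q from 0.3 to 0.6 and three other assumed mixes (55/25/15/5%, 25/25/25/25% and 10/25/35/30%), k explains 8–16% of outcome variance under independence, 3–7% at correlation 0.3 and 1–2% at 0.6. Simulated trials used 80 vs 80 men, the 35/30/20/15% mix and a Poisson model with log link. In them, adding k reduced the variance of the log risk ratio by about 8–13% under independence, 4–5% at correlation 0.3 and 0–2% at 0.6. These percentages carry simulation error.

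**The case against.** Four points on the other side deserve weight.

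- A reader might infer that sections 4.2 and 8.4.2.2 state two clear and opposed outcomes, or that 8.4.2.2 commits the trial to claiming recovery for men who still meet criteria for other disorders. The text does not go that far. Each sentence is ambiguous, so this is one unsettled definition.
- A reader might infer that the number of baseline diagnoses largely determines the outcome. The documents give neither the distribution of diagnoses nor remission rates. Even the favourable assumption of independent resolution gives at most about 16% of variance explained. The trial's transdiagnostic premise suggests that disorders in one person may resolve together, which lowers the figure.
- A reader might infer bias from the missing covariate. Randomization rules out systematic bias. What is lost is some precision and protection against chance imbalance, and section 8.2 leaves room for a sensitivity analysis on the latter. Reusing the primary binary method is defensible in itself.
- This is one of many secondary outcomes. Depression and anxiety are also measured on several scales with baseline adjustment, and no primary conclusion depends on the MINI outcome.

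All four stand as limits on the point. None of them supplies the missing definition or reconciles odds with a risk ratio. Section 8.2 offers adjustment only if imbalance is found and does not name diagnosis count.

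**Conclusion.** The point holds as a gap in specification. The MINI outcome has two readings that the documents do not reconcile, two effect measures, and no baseline diagnosis term where comparable outcomes have a baseline covariate. The first two follow from the text alone and need no assumed inputs.

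The size is illustrative. The risk ratio is 1.27 or 1.67 under the assumed remission rates, diagnosis mix and independence, and about 1.36 or 1.52 at a within-person correlation of 0.6. If nearly every man had a single baseline diagnosis, the readings would almost coincide.

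The covariate is the lesser part: a modest precision gain at best, close to nil if diagnoses resolve together. The documents do not favour one reading over the other, so either would resolve the ambiguity once stated.

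**What to change.** - Put one definition in sections 4.2, 8.4 and 8.4.2.2. One option is that none of the participant's baseline MINI diagnoses is present at the visit, with the other reading reported descriptively.
- List which MINI diagnoses count, since the SAP gives only examples.
- Replace odds with the risk ratio in sections 4.2 and 8.4, to match section 8.3.1.
- Pre-specify the number of baseline MINI diagnoses as a covariate for this outcome.

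This needs SAP wording only. The Protocol (Section VI, item 1 on information collected) already has the MINI given at baseline and at each follow-up.

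There are two costs. First, the stricter definition has fewer events. At 80 per arm, two-sided 0.05 and remission of 50% vs 35%, power across the three other assumed mixes is about 0.38–0.43, against 0.50–0.57 for the looser definition. With remission of 60% vs 40% the two are equal, at about 0.68–0.71, so the loss depends on the remission level. Second, the extra covariate may make the log-binomial model more likely to fail to converge, in which case the modified Poisson fallback already planned in section 8.3.1 applies.

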8.4.3 Minority Stress- Mediation analysis

We plan to model minority stress mediators (rejection sensitivity, internalized homophobia, sexual orientation concealment) as a latent variable at the 4- and 8-month time points. We will then use these constructs in latent variable mediation models using structural equation modeling to examine whether 4-month minority stress mediates 8-month sexual risk and mental health outcomes; and whether 8-month minority stress mediates 12-month sexual risk and mental health outcomes. The mediation models will include test of exposure-mediation interactions (Valeri and VanderWeele 2013; Muthan and Asparoutov 2015), to consider potential confounding of the mediation-outcome relationship and allow for causal interpretation. In case of support for a mediating effect of minority stress in the above latent variable mediation model, we will apply a sequential approach in our analyses of mediation to estimate both the joint effect through all mediations, as well as, give consideration to how much of the combined effect is attributed to each mediator (Vansteelandt and Daniel 2017; VanderWeele and Vansteelandt 2014).

